In a recent Cochrane review on the comparison of self-administered survey questionnaire responses collected using mobile apps versus other methods it was concluded that there are no data available on response rates. We will attempt to address this question.

RESEARCH DESIGN AND METHODS

Briefly describe study design and anticipated enrollment, i.e., number of subjects to be enrolled by researchers study-wide and by Partners researchers. Provide a brief summary of the eligibility criteria (for example, age range, gender, medical condition). Include any local site restrictions, for example, “Enrollment at Partners will be limited to adults although the sponsor’s protocol is open to both children and adults.”

All Patient Gateway naïve patients aged 18 years or older able to consent for themselves, admitted to the hospital for an orthopaedic condition with the need for outpatient follow-up and access to the internet or a smartphone will be invited to participate in this study. Exclusion criteria will be patients unable to consent for themselves, inability to communicate in English, and no possession of a smartphone.

We will collect 240 patients; 120 in each group. Existing follow-up is assumed to be close to 70%, to detect a 15% difference at 95% CI, N=240.

Briefly describe study procedures. Include any local site restrictions, for example, “Subjects enrolled at Partners will not participate in the pharmacokinetic portion of the study.” Describe study endpoints.

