Eligible patients will be randomized into two groups; one group that is enrolled while an inpatient and another group that is just provided information about how to enroll. All patients eligible for participation will be approached during their hospital stay and asked for consent. Patients will be cluster randomized by week and after consenting, they will be assigned to the treatment arm randomized to that specific week. For intervention group, an explanation on the app will be provided by a trained research staff member and they will be fully enrolled in the app in the presence of this research staff member. In the period between hospital discharge and follow-up, patients using the Gateway app will be requested to fill out a survey on their personal device and will receive a notification of their upcoming appointment. We will monitor when patients return to clinic for their first, 90-day, and 1-year follow-up outpatient appointments. At 90 day and 1 year follow-up outpatient appointments, patients from both groups will be invited to complete a survey on a hospital owned tablet device per standard clinic protocol. In addition to the standard survey, two brief questionnaires on satisfaction with the electronic application and satisfaction with overall care

will be provided at the end of the regular survey (if already completed over the app; just the satisfaction questions will be administered).

Descriptive statistics will be used for demographic data. Logistic regression will be used for binary outcome data.

For studies involving treatment or diagnosis, provide information about standard of care at Partners (e.g., BWH, MGH) and indicate how the study procedures differ from standard care. Provide information on available alternative treatments, procedures, or methods of diagnosis.

Not applicable as this study does not alter treatment or diagnosis in any way.

Describe how risks to subjects are minimized, for example, by using procedures which are consistent with sound research design and which do not unnecessarily expose subjects to risk or by using procedures already being performed on the subject for diagnostic or treatment purposes.

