The risk to subjects and their privacy is no more than minimal risk because all data that will be reviewed will be purely demographic and questionnaire data. Any protected (identifiable) health information will be de-identified when the study has been completed. PHI will be stored on a password-protected Partners network computer with access limited to study staff. We will be using REDCap to collect survey responses, which is hosted behind the Partners Firewall.

Describe explicitly the methods for ensuring the safety of subjects. Provide objective criteria for removing a subject from the study, for example, objective criteria for worsening disease/lack of improvement and/or unacceptable adverse events. The inclusion of objective drop criteria is especially important in studies designed with placebo control groups.

Subjects who indicate that they do not wish to participate will not be included in the study.

FORESEEABLE RISKS AND DISCOMFORTS

Provide a brief description of any foreseeable risks and discomforts to subjects. Include those related to drugs/devices/procedures being studied and/or administered/Performed solely for research purposes. In addition, include psychosocial risks, and risks related to privacy and confidentiality. When applicable, describe risks to a developing fetus or nursing infant.

The one risk we can foresee is a breach of patient confidentiality. We will take the utmost care to ensure that confidentiality is maintained. Patient specific identifiers will be erased once data is collected and verified. The identifiers will be assessable for the shortest duration of time possible.

EXPECTED BENEFITS

Describe both the expected benefits to individual subjects participating in the research and the importance of the knowledge that may reasonably be expected to result from the study. Provide a brief, realistic summary of potential benefits to subjects, for example, "It is hoped that the treatment will result in a partial reduction in tumor size in at least 25% of the enrolled subjects."

Indicate how the results of the study will benefit future patients with the disease/condition being studied and/or society, e.g., through increased knowledge of human physiology or behavior, improved safety, or technological advances.

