When specimens or data collected by research collaborators outside Partners will be sent to Partners investigators, indicate from where the specimens/data will be obtained and whether the specimens/data will contain identifiers that could be used by Partners investigators to link the specimens/data to individual subjects. When appropriate, submit documentation of IRB approval and a copy of the IRB-approved consent form from the institution where the specimens/data were collected.

No specimens/data will be received from sites outside of partners for future use.

Statistical analysis, study size

Descriptive statistics were used for demographic data. Differences between groups were assessed using the chi-square or Fisher's exact test for categorical variables and the t-test and/or analysis of variance (ANOVA) for continuous variables. Demographic or treatment factors associated with improved follow-up or EPP use were assessed using forward stepwise logistic regression modeling to avoid overfitting. We also performed a sub-group analysis assessing the effect of patient race and average median income. A robustness analysis exploring the likelihood of enrolling in an EPP or completing follow-up in all patients was also performed. Significance was set at $P < 0.05$. Stata software, version 14 (StataCorp), was used for all analyses.

An a priori power analysis was completed to determine sample size, we assumed an existing follow-up rate of 70%, and to detect an ~10% difference in follow-up with an alpha of 0.05, we calculated an approximate sample size of 200 patients distributed equally between both groups.

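### The plan names two different methods for binary outcomes, does not say which one compares the arms on follow-up, and plans no percentage-point difference with a confidence interval.

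*Combined protocol and SAP*

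**What the plan says.** Research Design and Methods, in the part on study procedures: "Logistic regression will be used for binary outcome data". No covariates and no effect measure are named. The same part states that treatment is randomised in clusters, the cluster being the week.

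Statistical analysis, study size: "Differences between groups were assessed using the chi-square" or Fisher's exact test when the variable is categorical. Then, as a separate step: "Demographic or treatment factors associated with improved follow-up or EPP use were assessed using forward stepwise logistic regression modeling to avoid overfitting". And: "We also performed a sub-group analysis assessing the effect of patient race and average median income". A robustness analysis of follow-up in all patients is also mentioned, without a method. The only criterion given is P < 0.05.

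The target effect appears twice. Research Design and Methods: "Existing follow-up is assumed to be close to 70%, to detect a 15% difference at 95% CI, N=240". The Statistical analysis section has the same 70% control rate but a difference of roughly 10% and about 200 patients.

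On what is recorded at baseline, the section on minimising risk says that "all data that will be reviewed will be purely demographic and questionnaire data".

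**The concern.** Whether patients return to clinic is the first aim, and return by arm is a between-group difference in a categorical variable. So the Statistical analysis section, read naturally, sends the main comparison to chi-square or Fisher, while the protocol section sends it to logistic regression. The choice is left open.

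Three things are at stake.

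- **No fixed arm estimate.** Demographics enter a forward stepwise model and subgroup analyses. Forward selection guarantees neither that arm stays in the model nor which covariates accompany it, so it does not supply a prespecified adjusted arm effect.
- **No effect on the planning scale.** Chi-square and Fisher give a P value and logistic regression gives an odds ratio. A non-significant result then cannot be read against the planned difference.
- **Week is ignored.** None of the named methods, as described, accounts for the unit of randomisation.

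**Working it through.** **Inputs.** From the documents: control rate 70%; 15 points with 120 per arm (Research Design and Methods); about 10 points with 100 per arm (Statistical analysis); alpha 0.05. Not stated, so assumed: two-sided testing, 80% power, patients per week, ICC, covariate strength.

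**1. The plan's own sample sizes.** n per arm = [1.96·√(2p̄(1−p̄)) + 0.842·√(p1(1−p1)+p2(1−p2))]² / (p2−p1)².

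- 70% v 85%, p̄ = 0.775: 121 per arm, 242 in total. The stated 240 is reproduced; power at 120 per arm is 79.8%.
- 70% v 80%, p̄ = 0.75: 294 per arm, 588 in total. The stated 200 is not reproduced; power at 100 per arm is 37%.

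The two planned differences therefore cannot both serve as the benchmark.

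**2. Does the choice of unadjusted method matter?** Exact enumeration of all 2x2 tables, 120 per arm, 70% v 85%, independent patients: power is 80.5% for chi-square, 75.9% for Fisher and 79.8% for the logistic Wald test. Chi-square and Wald disagree at 0.05 in 0.8% of trials. Fisher is the one that differs noticeably.

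**3. What a percentage-point estimate would show.** Half-width = 1.96·√(p1(1−p1)/n + p2(1−p2)/n).

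- 120 per arm, 70% v 85%: 1.96·√(0.21/120 + 0.1275/120) = 10.4 points, so 4.6 to 25.4. The same rates give OR (0.85/0.15)/(0.70/0.30) = 2.43 but RR 0.85/0.70 = 1.21.
- 100 per arm, 70% v 80%: 11.9 points, so −1.9 to 21.9.

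Two non-significant results at 120 per arm:

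| Returning | Chi-square P | Difference (95% CI), points | 15 points excluded? |
|---|---|---|---|
| 84 v 96 | 0.07 | +10 (−0.9 to 20.9) | no |
| 84 v 84 | 1.00 | 0 (−11.6 to 11.6) | yes |

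Under P < 0.05 alone, both are just not significant.

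**4. Gain from prespecified adjustment** (120 per arm, 70% v 85%, independent patients). Multiplying the variance by (1−R²):

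| Assumed R² | Power | Half-width, points |
|---|---|---|
| 0 | 79.8% | 10.4 |
| 0.02 | 80.6% | 10.3 |
| 0.05 | 81.8% | 10.1 |
| 0.10 | 83.9% | 9.9 |
| 0.20 | 87.9% | 9.3 |

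Simulation (3,000 trials per setting) of unadjusted chi-square v adjusted logistic regression, with four factors of joint AUC 0.63, 0.70 and 0.76, gave 80.8 v 81.8%, 79.1 v 82.7% and 80.5 v 85.4%. A further simulation gave gains of about 0 to 7 points. Unadjusted power should be the same in all three settings yet ranges from 79.1 to 80.8%, so the smallest gain is within simulation noise. These runs test the adjusted logistic coefficient; they do not measure the precision of a standardised risk difference.

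**5. Clustering by week.** Design effect = 1 + (m−1)·ICC, and power is recomputed at 120/(design effect) per arm.

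| Patients per week | ICC | Design effect | Power | Half-width, points |
|---|---|---|---|---|
| 3 | 0.01 | 1.02 | 79% | 10.5 |
| 10 | 0.02 | 1.18 | 73% | 11.3 |
| 10 | 0.05 | 1.45 | 64% | 12.5 |

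A test that ignores week would have true two-sided error 2·Φ(−1.96/√DE): 2·Φ(−1.80) = 7% at 1.18 and 2·Φ(−1.63) = 10% at 1.45.

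**The case against.** The strongest reply is that the plan does use demographics. They go into a logistic model for follow-up, and race and income have a subgroup analysis. The phrase about treatment factors could even include assigned arm. This stands against a stronger reading that a reader might infer, namely that baseline data are left unused. They are not; what is missing is a fixed covariate set and a guaranteed arm term in the comparison that answers the aim.

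Nor does the conflict of methods cause the lack of adjustment. Logistic regression could carry covariates and yield a risk difference; the plan just does not say so.

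The Statistical analysis section does not expressly tie chi-square or Fisher to follow-up, and the sentence could also cover baseline comparisons. That is true, so the unadjusted 2x2 test is the natural reading and not a stated rule. But if the sentence covers only baseline tables, that section names no arm comparison at all.

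Chi-square and unadjusted logistic regression almost always agree. This stands: the conflict is mainly one of specification.

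A reader might also infer that chance imbalance in demographics biases the result. It does not. Under randomisation it is sampling error, which valid standard errors cover. The case for adjustment is precision.

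Finally, the section is written in the past tense. If outcomes had already been examined, covariates chosen afterwards would be post hoc and should be labelled so.

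**Conclusion.** The point holds as a gap in specification that should be closed; it does not show that the trial's result would be wrong. The two sections name different methods without saying which compares the arms on follow-up. No prespecified adjusted arm effect and no risk difference with a confidence interval is planned, and none of the named methods is said to account for week.

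The lack of an interval on the planning scale is certain from the text. Its importance follows from a half-width of about 10 to 12 points, against planned differences of 15 or about 10. The gain from adjustment is modest, roughly 0 to 7 power points at 120 per arm and 70% v 85%, and depends on covariate strength that the documents do not give. Clustering may outweigh it: 1 to 16 power points over 3 to 10 patients per week and ICC 0.01 to 0.05, all assumed.

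**What to change.** For each binary outcome (return to clinic, survey completion), name one primary analysis:

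- Logistic regression on assigned arm, with arm always in the model.
- A short fixed list of demographic factors already collected, kept whatever their P values and not chosen stepwise. Race and median income are named in the plan; age and sex could be added if recorded. At 70% and 85%, 0.30·120 + 0.15·120 = 54 non-returns are expected, so about five covariate terms is a sensible ceiling.
- Standard errors that account for week, with a small-sample correction if weeks are few. At 10 patients per week, 240 patients are only 24 weeks.
- The standardised difference in percent returning with its 95% CI, read against the planned difference. First reconcile 15 points and 240 patients with about 10 points and 200 patients.

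Any unadjusted sensitivity analysis should account for week too, so a plain chi-square will not do. The stepwise model can remain as exploratory work.

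The cost is SAP wording and a few lines of Stata, with no new data. The covariate list and the handling of missing baseline values must be fixed in advance, and week-level standard errors may widen the interval.

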Protocol Summary and Statistical Analysis Plan

Does inpatient enrollment into a patient communication app (Patient Gateway) result in improved follow-up and survey completion rates after orthopaedic trauma?

NCT2017P001594

Version Date 03/07/2018

**PARTNERS HUMAN RESEARCH COMMITTEE
PROTOCOL SUMMARY**

Answer all questions accurately and completely in order to provide the PHRC with the relevant information to assess the risk-benefit ratio for the study. Do not leave sections blank.

PRINCIPAL/OVERALL INVESTIGATOR

[name], MPH, FRCSC

PROTOCOL TITLE

Does inpatient enrollment into a patient communication app (Patient Gateway) result in improved follow-up and survey completion rates after orthopaedic trauma?

FUNDING

Department Funding

VERSION DATE

3/7/2018

SPECIFIC AIMS

Concisely state the objectives of the study and the hypothesis being tested.

This study aims to:

1. To determine if inpatient enrollment into a patient communication app (Patient Gateway) improves clinic follow-up of orthopaedic trauma patients.
2. To determine if inpatient enrollment into a patient communication app (Patient Gateway) improves survey completion rates after orthopedic trauma.

BACKGROUND AND SIGNIFICANCE

Provide a brief paragraph summarizing prior experience important for understanding the proposed study and procedures.

Follow-up in trauma is historically poor. As a result, outcomes from trauma are difficult to collect via surveys and are often significantly influenced by selection bias. Patient interaction apps like Patient Gateway are thought to facilitate greater participant involvement and adherence to treatment regimens. We explored if inpatient enrollment into Patient Gateway would improve clinic follow-up rates. Increasing follow-up rates could improve the quality of care delivered.

In addition, self-administered survey questionnaires are an important data collection tool in clinical practice, public health research and epidemiology. However, survey completion rates are typically poor in orthopaedic trauma.

With the evaluation of modern technology, electronic applications are being increasingly used in both hospital and personal settings. In our outpatient clinic, questionnaires to measure outcomes and monitor quality of care are

administered by staff members using hospital owned tablet devices. Recently, applications to complete these surveys on personal devices have been developed.

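### Forward stepwise selection will exaggerate the reported factors for follow-up and EPP use; fit one fixed model and report every term

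*Combined protocol and SAP*

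**What the plan says.** The section on statistical analysis and study size, at the end of the combined document, describes the factor analysis in one sentence: "Demographic or treatment factors associated with improved follow-up or EPP use were assessed using forward stepwise logistic regression modeling to avoid overfitting". The only threshold in that section is general: "Significance was set at $P < 0.05". It lists no candidate variables, entry or removal rule, cap on the number of terms, shrinkage or validation. It does not call the search exploratory, and it does not say whether the randomized arm is one of the candidate treatment factors. EPP is not expanded.

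The arm comparison is described separately: "Differences between groups were assessed using the chi-square or Fisher's exact test for categorical variables". Race and income also appear in a subgroup analysis: "We also performed a sub-group analysis assessing the effect of patient race and average median income".

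The protocol, under Research Design and Methods, says only "Logistic regression will be used for binary outcome data" and mentions no variable selection. The first of the Specific Aims concerns the arm effect: "To determine if inpatient enrollment into a patient communication app (Patient Gateway) improves clinic follow-up of orthopaedic trauma patients".

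**The concern.** A factor enters a forward stepwise model because its estimate happens to be large relative to its standard error in this sample. If it is then read as though the model had been fixed in advance, the estimate is biased away from the null and the usual interval ignores the search. The bias comes from reporting only what passes the filter, and stepwise selection builds that filter in.

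The list of factors said to be associated with follow-up or EPP use is at stake. Real factors would be reported with exaggerated odds ratios, while the stated rationale would lead a reader to think the method had dealt with the problem.

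**Working it through.** The documents give no figure for this model, so there is none to reproduce. They supply only the data size.

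**Inputs from the documents.** SAP: 200 patients, 70% against about 80% follow-up. Protocol: 240 patients, 70% against 85%. Expected non-attenders:
- SAP design: 100×0.30 + 100×0.20 = 50
- protocol design: 120×0.30 + 120×0.15 = 54
- protocol N with no arm effect: 240×0.30 = 72

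**Assumed.** 8 or 12 independent binary demographic candidates, one of them real at OR 1.5 and the rest noise; prevalence 50%; the arm also a candidate; forward Wald entry at P<0.05 with no removal step; independent patients.

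**Hand check for one factor, N = 200.** Average follow-up is (0.70+0.80)/2 = 0.75.
- SE of log OR = √{2×[1/(100×0.75) + 1/(100×0.25)]} = 0.327
- expected z = ln(1.5)/0.327 = 0.405/0.327 = 1.24
- P(retained) = P(Z > 1.96−1.24) + P(Z < −1.96−1.24) = 0.236 + 0.001 = 0.237
- mean z if retained = 1.24 + (0.308−0.002)/0.237 = 2.53, so the mean reported OR = exp(2.53×0.327) = 2.29
- coverage if retained = [P(Z > 0.72) − P(Z > 1.96)]/0.237 = (0.236−0.025)/0.237 = 0.89

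The same steps at true OR 2.0 (expected z = 0.693/0.327 = 2.12) give a retained OR of 2.51 and coverage of 0.956.

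**Simulation, 60,000 trials per cell (coverage SE about 0.003).**

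| | N=200, 8 | N=200, 12 | N=240, 8 | N=240, 12 |
|---|---|---|---|---|
| Real factor retained | 0.228 | 0.225 | 0.243 | 0.244 |
| Stepwise OR if retained (truth 1.5) | 2.39 | 2.41 | 2.32 | 2.33 |
| Coverage if retained | 0.887 | 0.885 | 0.889 | 0.887 |
| Full model, all terms reported: OR | 1.54 | 1.56 | 1.53 | 1.55 |
| Full model, filtered at P<0.05: OR | 2.47 | 2.53 | 2.37 | 2.42 |
| Six fixed terms, all reported: OR | 1.53 | 1.53 | 1.52 | 1.53 |
| Six fixed terms: coverage | 0.950 | 0.950 | 0.948 | 0.948 |

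The six terms are the arm and five demographics. The filtered full model is as inflated as stepwise, so reporting every term is what removes the bias. Repeats with fewer trials scatter over roughly 86-92% coverage. A variant with 10 candidates and no arm (800 trials per cell, so only 215 and 227 retained) gave OR 2.27 and 2.12, with coverage 88% and 94%.

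**Sensitivity (8 candidates, N=200/N=240).**
- True OR 2.0: retained OR 2.63/2.55, coverage 0.953/0.955.
- Entry at 0.10: 2.20/2.15, coverage 0.915/0.924.
- Entry at 0.20: 2.03/1.97, coverage 0.925/0.933.
- Prevalence 25%: 3.07/2.97, coverage 0.868/0.866.

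**Overfitting (calibration slope on new data; 1.0 means none).** Stepwise, in trials that keep at least one term, against entering all candidates:
- N=200: 0.37 against 0.31 (8 candidates), 0.31 against 0.22 (12)
- N=240: 0.72 against 0.52 (8), 0.66 against 0.40 (12)

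The six-term model gives 0.42-0.43 at N=200 and 0.64-0.65 at N=240. Its figures are not restricted to trials that keep a term, so the comparison with stepwise is approximate.

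**The case against.** The strongest defence is that the rationale should be read against the obvious alternative of entering every candidate. On that comparison stepwise is less overfit in all four cells. The fixed six-term model does not clearly beat it at N=240. This stands. A reader might infer that stepwise selection makes overfitting worse, or that the replacement would predict better; neither is supported. What remains is that overfitting is reduced and not avoided, and that the reported estimates are biased by selection.

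Three further points also stand:
- **Noise factors.** At least one enters in 30% of trials (8 candidates) or 42-43% (12). This is ordinary multiplicity: 1−0.95^7 = 30.2% and 1−0.95^11 = 43.1%. A full fixed model tested at P<0.05 does about the same, so these rates are not a fault peculiar to stepwise.
- **Output.** The SAP does not say that odds ratios or intervals will be reported from this model. They are its usual output, so that part is a consequence and not quoted text. P-value entry is likewise inferred from the method's name and the general threshold.
- **Magnitude.** Every size above depends on assumed candidates, prevalence and entry rule.

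A reader might also infer that the trial's main result is compromised. It is not: the arms are compared by a separate test that involves no selection. Only if the arm is a stepwise candidate, which the SAP leaves unclear, would a stepwise arm estimate be affected. In that case its retained OR would average about 2.5 against a truth of 1.71 in the SAP design (1.75-1.76 if forced in), and 2.8 against 2.43 in the protocol design (2.52 if forced in).

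**Conclusion.** The point holds as selection bias in a secondary analysis. Under the stated assumptions a real factor with OR 1.5 is reported in about a quarter of trials, at an average OR of 2.3-2.4 with interval coverage of roughly 86-92%. The same factor in a fixed model with every term reported averages 1.52-1.53 with about 95% coverage. Inflation persists in every condition tried (retained OR from about 2.0 to 3.1 at a truth of 1.5). The under-coverage is modest and vanishes at a true OR of 2.0. The direction is secure; the exact size is not, because the candidate list and entry rule are not stated. The change is worth making because it is cheap and the stated rationale claims more than the method delivers.

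**What to change.** Remove forward stepwise selection and its rationale. For follow-up:
- Fit one logistic model with the arm forced in and a short list of demographics already collected (for example age, race and median income), chosen without reference to the outcome data. Keep it small for 50-72 expected non-attenders; the six terms simulated here leave 50/6 = 8 to 72/6 = 12 per term.
- Use standard errors that allow for clustering by randomization week, since the protocol randomizes weeks and not patients. The simulations above ignore this.
- Report every term with its 95% CI whatever its P value, and label the factor results exploratory, without multiplicity control.
- The SAP is written in the past tense. If the analysis has been run, say that the list was set afterwards.

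Use the same list for EPP use. If use means enrolment, fit that model in the information-only arm and without an arm term. Intervention patients are enrolled by staff ("they will be fully enrolled in the app in the presence of this research staff member"), so the arm would determine the outcome by design. That leaves 100 or 120 patients, so intervals will be wide.

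The cost is SAP wording, possibly a re-run, and giving up data-driven selection. No new data are needed. The change removes the selection bias in the reported estimates. It does not remove multiplicity, and it is not claimed to predict better than stepwise.

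### The statistical section does not name survey completion, the Aim 2 endpoint; only generic test lines could reach it, with no time point, survey route or denominator

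*Combined protocol and SAP*

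**What the plan says.** The title asks whether inpatient enrolment will "result in improved follow-up and survey completion rates after orthopaedic trauma". Specific Aims gives survey completion an aim of its own: "To determine if inpatient enrollment into a patient communication app (Patient Gateway) improves survey completion rates after orthopedic trauma".

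Research Design and Methods (study procedures) describes two survey routes. Patients using the app are asked for a survey on their own device between discharge and follow-up. At the 90-day and 1-year appointments, both groups are invited to complete a survey on a clinic tablet; anyone who has already done it on the app gets only the satisfaction questions. The same section says of the intervention group that "they will be fully enrolled in the app in the presence of this research staff member", while controls only receive information on how to enrol. Its analysis text on outcomes is one sentence: "Logistic regression will be used for binary outcome data".

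The section Statistical analysis, study size names outcomes for modelling in two sentences: "Demographic or treatment factors associated with improved follow-up or EPP use were assessed" (by forward stepwise logistic regression) and "A robustness analysis exploring the likelihood of enrolling in an EPP or completing follow-up in all patients was also performed". Its general between-group line is "Differences between groups were assessed using the chi-square or Fisher's exact test for categorical variables". The word survey does not occur in the section. Both sample size statements concern follow-up only.

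**The concern.** One of the two stated aims has no named endpoint in the section that governs the analysis. An analyst who runs only the analyses named there would report clinic attendance and EPP use or enrolment, and could leave out survey completion without departing from any named outcome. If survey completion is analysed under the generic lines, its definition is open: which time point, whether app surveys count, and whether non-attenders are in the denominator. Those choices could be made after the data are seen, and they can change the result.

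A second risk is that a reader takes an arm difference in EPP enrolment as support for the trial's second question. Enrolment is what staff deliver to the intervention arm, so it shows that the intervention was given and does not show that more surveys came back.

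**Working it through.** The plan states no figure for survey completion, so there is none to reproduce. The check is mainly textual, with short arithmetic to show that the open choices matter.

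**1. Aims against named outcomes.**
- Aim 1, clinic follow-up: named in the modelling sentence, the robustness sentence and both sample size statements.
- Aim 2, survey completion: named in none of these.
- EPP use or enrolment: named in the modelling and robustness sentences, but not an aim.

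**2. Denominator.** Inputs from Research Design and Methods: 120 per group, 70% existing follow-up, 15% difference (read as percentage points in favour of the intervention). Assume that these rates apply at the visit where the tablet survey is offered (the protocol does not tie the 70% to a visit), that only tablet surveys count, and that the same proportion c of attenders completes the survey in both arms.
- Attenders: control 0.70 × 120 = 84; intervention 0.85 × 120 = 102.
- Attenders as denominator: 84c/84 = c against 102c/102 = c, a difference of 0.
- All assigned patients as denominator: 84c/120 = 0.70c against 102c/120 = 0.85c, a difference of 0.15c, or 15c percentage points.
- With the roughly 10-point difference in the statistical section: 0.80c − 0.70c = 0.10c, or 10c points.

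The same data thus give no effect under one denominator and an effect under the other. The attender denominator also conditions on the Aim 1 outcome.

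**3. Route.** On the same inputs, 120 − 84 = 36 controls and 120 − 102 = 18 intervention patients do not attend, and only an app survey could make them completers. Among attenders, someone who already completed the survey on the app is not given it again on the tablet. A tablet-only count would therefore record that person as a non-completer. App requests go only to app users, and staff enrol the intervention arm, so this misclassification would not be balanced between arms.

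**4. EPP enrolment as an outcome.** Suppose every intervention patient is enrolled, as the procedures intend, and m of n controls are not. Fisher's two-sided p = 2 × C(n, m) / C(2n, m).
- n = 100: m = 6 gives 2 × 0.0145 = 0.029; m = 5 gives 2 × 0.0297 = 0.059.
- n = 120: m = 6 gives 2 × 0.0147 = 0.029; m = 5 gives 2 × 0.0300 = 0.060.

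Six unenrolled controls are enough for p < 0.05, that is, control enrolment as high as 94% (94/100) or 95% (114/120). The logistic odds ratio for arm is not finite in this case. The test ignores weekly clusters and serves only as an illustration.

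**5. Power.** No survey completion rate is given. For assumed control rates of 20% to 70%, two-sided power for a 15-point gain is 57% to 72% at 100 per arm and 65% to 80% at 120 per arm, before any allowance for clusters.

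**The case against.** The best reply is that survey completion is already covered. It is a yes/no variable and the trial has two groups, so the chi-square or Fisher line in the statistical section applies to it. The logistic regression sentence in the study procedures stands as well: this is one document with one version date, and nothing says that the later section replaces the earlier. The surveys are collected. This stands in part. A comparison by arm is available in generic form, so a reader who infers that Aim 2 cannot or will not be answered goes further than the documents allow. But a generic test fixes no time point, route or denominator.

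A reader might also infer that EPP use has replaced survey completion as the second outcome. The documents do not say so. The first sentence concerns factors associated with follow-up or EPP use, chosen by stepwise selection, and the second is a robustness analysis. Neither is labelled as the analysis of an aim, and neither presents EPP use as an effectiveness endpoint.

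A third tempting inference is that EPP use is produced by design. That holds for enrolment only. Use is undefined and could mean later activity, which is up to the patient. Nor do the documents give a self-enrolment rate for controls, so the size of the arm difference in enrolment cannot be stated.

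Finally, the statistical section is in the past tense. If the analysis is finished, an endpoint defined now is post hoc. That is a reason to disclose its timing and does not justify omitting it.

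**Conclusion.** The point holds in a limited form. The statistical section does not name survey completion, one of the trial's two aims, and only generic lines could reach it, without time point, route or denominator. The gap is material: on the protocol's planning rates, the denominator alone moves the arm difference between 0 and 15c percentage points, where c is the tablet completion proportion among attenders, assumed equal in the two arms. That figure is an illustration and does not estimate the error in the trial's result.

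EPP enrolment cannot stand in for Aim 2, because it is receipt of the assigned intervention. This rests on reading EPP as Patient Gateway, the only such product in the documents. The verdict does not extend to later EPP use, which is undefined, and it does not claim that Aim 2 was abandoned.

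**What to change.** In Statistical analysis, study size:
- Name survey completion (yes/no) at 90 days and at 1 year as the Aim 2 endpoint. Count completion by either the app or the clinic tablet, and state the window in which an app survey counts towards each time point.
- Compare it by the arm assigned to the week of enrolment, with all consented and assigned patients in the denominator. Non-attenders without a survey count as not completed.
- Use an analysis that allows for cluster randomisation by week, such as a logistic model with a random effect for week or standard errors clustered on week. Report the arm difference with a confidence interval, since no power was planned for this endpoint.
- Define EPP, and report EPP enrolment or use descriptively as an uptake measure.
- If the analysis is already done, state that this definition was added afterwards.

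The cost is some wording and one more table from data that the protocol already collects. The small downside is that EPP enrolment can no longer be presented as an effectiveness outcome.
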